#### 6.2 Exclusion criteria

• Perforated gastric ulcer or duodenal ulcer treated within 24 hours of the onset of symptoms

- Traumatic injury to the bowel (including iatrogenic or intra-operative) treated within 12 hours of injury
- Uncomplicated diverticulitis defined as an episode with a short history and with clinical signs of diverticulitis, with an increased body temperature and inflammatory parameters, verified by computed tomography (CT), and without any sign of complications such as abscess, free air or fistula.
- Grade 4 or 5 appendicitis defined by the 2017 American Association for the Surgery Trauma Grading System with either generalised peritonitis at surgery, or no or partial source control e.g. radiological drainage
- Non-perforated cholecystitis
- Ischemic or necrotic intestine without perforation
- Uterine perforation following uterine surgery treated within six hours of injury
- clAls with a low risk of complications who may receive more than 72 hours antibiotics are not intended to be included (such as those listed above: Traumatic injury to the bowel (including iatrogenic or intra-operative) treated within 12 hours of injury, Uterine perforation following uterine surgery treated within six hours of injury, Perforated gastric ulcer or duodenal ulcer treated within 24 hours of the onset of symptoms). Clinician assessment on the eligibility of patients receiving more than 72 hours of in-patient surgical care and antibiotics for their clAl may be required in patients who have clinically improved at this point and do not require active surgical care but remain in hospital and on antibiotics
- Current enrolment in another trial dictating antibiotic treatment duration
- Previous *Clostridium difficile* infection
- Infected necrotic pancreatitis
- Concomitant infection requiring ≥4 weeks antibiotic therapy including Intra-hepatic abscess/es
  planned to be treated with fixed-extended-duration antibiotics of 4 to 6 weeks antibiotics,
  osteomyelitis, and endocarditis
- Peritoneal dialysis
- Previously recruited for the EXTEND trial
- Treatment with Interleukin-6 Inhibitors
- High likelihood of death within 72 hours of randomisation in the opinion of the local Investigator
- Limitations in treatment decided before inclusion. Limitations in treatment that exclude patients from the EXTEND trial are those clinical decisions linked to an expectation the patient will die during this episode of infection.
- Patient with persistent cIAI of more than 6 months duration

• A maximum of 20% of participants entering the trial can have a source of cIAI as the appendix. If 230 patients with appendix as the source are recruited, this will become an exclusion criteria for subsequent patients.

Note: There are absolute exclusions that preclude trial participation. These include: C. difficile infection, Infected necrotic pancreatitis, Concomitant infection requiring ≥4 weeks antibiotic therapy, Treatment with Interleukin-6 Inhibitors, High likelihood of death within 72 hours of randomisation, Limitations in treatment decided before inclusion, Peritoneal dialysis, Previously recruited for the EXTEND trial, Patient with persistent cIAI of more than 6 months duration and a patient with persistent cIAI of more than 6 months duration. If a patient has two intraabdominal infections, the presence of one of the following ineligible infections does not make a patient ineligible if the other cIAI is eligible: Perforated gastric ulcer or duodenal ulcer treated within 24 hours of the onset of symptoms, Traumatic injury to the bowel (including iatrogenic or intra-operative) treated within 12 hours of injury, Uncomplicated diverticulitis, Ineligible cases of appendicitis (see exclusion criteria above), Uncomplicated cholecystitis, Ischemic or necrotic intestine without perforation, Uterine perforation following uterine surgery treated within six hours of injury or cIAI with a low risk of complications.

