Days of prescribed antibiotic therapy: Electronic medical records will be accessed to determine antibiotic (anti-bacterial) prescriptions in hospital and in the community where available. This data will be supplemented with self-reported antibiotic use at day 30, 90 and 180. Data on anti-fungal treatment will be collected to assess rates of fungal infections e.g., vulvo-vaginal candidiasis.

Others: All-cause mortality, length of hospital stay; re-admission and *C. difficile* infection will be assessed at day 180 after randomisation by review of hospital, medical records and interview with participants.

An episode of Acute Kidney Injury (Y/N): Increase in serum creatinine by  $\geq 0.3$  mg/dl ( $\geq 26.5 \mu$ mol/l) within 48 hours; or increase in serum creatinine to  $\geq 1.5$  times baseline, which is known or presumed to have occurred within the prior 7 days; or urine volume < 0.5 ml/kg/h for 6 hours (KDIGO Clinical Practice Guideline for Acute Kidney Injury).

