### C. difficile infection

The proportion of patients that experience C. difficile infection during the 180 days following randomisation will be reported by randomised group. This outcome will be modelled using a mixed effect logistic regression model with fixed effects for allocation, the stratification factors and other prognostic baseline covariates, and random intercepts for study recruitment site. The estimated conditional odds ratio for allocation, 95% confidence interval and p-value will be reported. To aid interpretability, point estimates and appropriate two-sided 95% confidence intervals for the relative risk (cases/non-cases) and absolute risk reduction (based on the fitted model) will be reported, with the fixed effect covariates in the model set to various representative values (i.e. marginal risk ratios and risk differences at representative values). Average marginal effects on both the risk ratio and risk difference intervals.

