# Appendix 3 – Data collected at baseline

Variable	Options	Person completing data point	Rules/References/Calculation	Form for analysis and how will be
				reported (continuous, categorical, ordinal)
Age	Years	RN		Continuous
Sex	Male/Female	RN	Sex as recorded in a patient's medical notes	Categorical
Race/Ethnicity	Standard option set	RN		Categorical
Centre	Name of site	RN		Categorical
Height/weight/body mass index	Centimetres/Kg/Ratio	RN	The measurements closest to the time of recruitment. Where data is missing state data missing	Continuous
Co-morbidities	Charlson score	RN	This data will be collected prospectively based on case note review and patient responses.	Continuous/ ordinal
cIAI severity	NEWS2/SOFA	RN		Continuous/ ordinal
Organ associated with the infection	Abdominal wall Appendix Biliary tract Gallbladder Large bowel Meckel's diverticulum Oesophagus Pancreas Reproductive tract Rectum Small bowel Stomach Urinary tract No specific organ identified Unknown	RN/Clinician	List all organs associated with the cIAI based on Ct or surgical findings.	Categorical
Underlying pathology	Adnexal abscess communicating with peritoneal cavity Anastomotic leak Appendicitis Complicated cholecystitis (perforation or extra-biliary abscess): calculous Complicated cholecystitis: acalculous Cancer-Appendix Cancer-Appendix Cancer-Bowel Cancer-Gynaecological Cancer-Gynaecological Cancer-Other Chemo-radiotherapy in last 12 months Clostridium difficile colitis Crohn's disease Diverticular disease Diverticular disease Drug reaction Fistula: Colo-urinary, Colo-intra- abdominal, Colo-cutaneous or Colo-vaginal Ischaemic bowel Immunosuppression	RN/Clinician		Categorical

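### Section 6.2 and Appendix 3 disagree on whether a patient with current C. difficile infection may enter, and the C. difficile outcome does not separate infection present at randomisation from new infection

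*Protocol*

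**What the plan says.** Three places in the Protocol bear on eligibility, and two on the outcome.

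- **Section 6.2, bulleted exclusions:** "Previous *Clostridium difficile* infection". No time window is given and current infection is not mentioned.
- **Section 6.2, closing Note:** "There are absolute exclusions that preclude trial participation. These include: C. difficile infection, Infected necrotic pancreatitis". The word *previous* is absent. The Note then lists infections that can be disregarded when the patient also has an eligible cIAI ("the presence of one of the following ineligible infections does not make a patient ineligible if the other cIAI is eligible"). C. difficile is not on that list.
- **Appendix 3, underlying pathology:** the options include "Clostridium difficile colitis".
- **Section 3.6:** C. difficile "infection will be assessed at day 180 after randomisation by review of hospital, medical records and interview with participants".
- **Section 10.2.4, C. difficile infection:** "The proportion of patients that experience C. difficile infection during the 180 days following randomisation will be reported by randomised group". A mixed effect logistic model follows, reported as a conditional odds ratio together with relative risk and absolute risk reduction.

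Neither outcome passage says whether infection already present at randomisation counts.

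**The concern.** Consider a patient whose cIAI is a colonic perforation in the course of current C. difficile colitis. Consider also one whose C. difficile infection is diagnosed during the antibiotic treatment that section 6.1 allows before randomisation (up to 10 days). A site working from the bullet may conclude that neither infection is *previous* and enrol. A site working from the Note will refuse. The baseline form has a box for the first patient, which does nothing to correct the first site.

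Two things are at stake. Sites need a single answer: section 7.2.1 has them confirm each eligibility criterion before randomisation, and section 13.4 does not accept enrolment outside the criteria. The second is how the harm comparison is read. Infections are among the serious adverse events exempt from reporting (section 9.3), and Appendix 6 lists infection of the GI tract, so this secondary outcome is where a difference in C. difficile between durations would mainly be seen. A case active at entry is an event whichever arm it falls in, and carries no information about the effect of duration.

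**Working it through.** **Step 1: the passages side by side.** The eligibility question is one of text, with no stated figure to reproduce.

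| Place | Past infection | Infection current at randomisation |
|---|---|---|
| 6.2 bullet | excluded | not addressed |
| 6.2 Note | within the unqualified wording | excluded on plain reading, no waiver |
| Appendix 3 | silent | colitis selectable as underlying pathology |
| 3.6 and 10.2.4 outcome | not applicable | not separated from new infection |

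Bullet and Note can be applied together only if the Note is read as widening the bullet. The Note can also be read as shorthand for it, since it abbreviates other items. The Appendix 3 option fits poorly with the wider reading. Other options that resemble exclusions keep an eligible form, such as ischaemic bowel with perforation, or a peptic ulcer treated beyond the time limit. C. difficile colitis has none under the Note.

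**Step 2: direction of any effect on the outcome.** Suppose k prevalent cases per arm are counted as events, equal between arms in expectation because of randomisation. The protocol gives no C. difficile rates, so every input here is an assumption except the 524 per arm, which comes from section 10.1. Take new infections of 10 (extended) v 5 (standard) per 524.

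- Risk ratio = (10 + k)/(5 + k). At k = 0 it is 10/5 = 2.00. At k = 2 it is 12/7 = 1.71, at k = 5 it is 15/10 = 1.50, and at k = 10 it is 20/15 = 1.33.
- Risk difference = [(10 + k) − (5 + k)]/524 = 5/524 = 0.95 percentage points for every k.

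**Step 3: the same check in proportions.** Let p be the control risk of new infection, 2p the risk in the extended arm, and q the share of each arm with prevalent infection. The observed risk ratio is [q + (1 − q)2p]/[q + (1 − q)p].

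| p (assumed) | q = 0.5% | q = 1% | q = 2% |
|---|---|---|---|
| 1% | 1.67 | 1.50 | 1.33 |
| 3% | 1.86 | 1.75 | 1.60 |
| 5% | 1.91 | 1.83 | 1.71 |

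The odds ratio behaves alike. At p = 1% it falls from 2.02 to 1.68, 1.51 and 1.34 across the same values of q.

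In this version the risk difference is (1 − q)p, so it shrinks by at most 2% of its own value at q = 2%. For scale, 0.5% of 524 is 2.6 patients per arm and 2% is 10.5. The upper end is hard to believe for a condition that at least one passage bars outright.

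**The case against.** The best case on the other side is that bullet and Note belong to one section. Read together, they bar both past and current infection. The Note calls its list absolute and gives C. difficile no waiver, and a delegated clinician confirms eligibility. An active case then enters only if a site overlooks the Note. Appendix 3 is a broad pick-list, with entries such as drug reaction and immunosuppression, and grants no eligibility. Section 10.2.4 leaves detailed specification of the secondary analyses to the SAP, which is not at hand. Absolute risk reduction is reported as well, and it is barely affected.

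Much of this stands. A reader might infer that the protocol lets active cases in, and that Appendix 3 confirms it. The documents do not support that: the plain wording of the Note bars them, and a data-collection option confirms no rule. Nor does the protocol call C. difficile the main harm of longer treatment. It is one item in an unranked list of secondary outcomes.

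Three things survive:

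- The listed criterion, which sites must confirm, says something narrower than the Note, and no SAP can repair eligibility text.
- The first effect measure named for this outcome is a conditional odds ratio, which is the kind of measure that is attenuated.
- The baseline pathology field could identify a colitis that caused the cIAI. An infection acquired during pre-randomisation antibiotics would be found only if it was recorded elsewhere, for example under other infection.

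**Conclusion.** The point holds as an inconsistency in an operative eligibility rule. Depending on the passage a site applies, a patient with current C. difficile infection may be enrolled or refused. If enrolled, the patient would count as an event under sections 3.6 and 10.2.4 as worded. The consequence is conditional on such enrolment. It would attenuate the odds and risk ratios and leave the expected risk difference essentially intact, probably through few patients.

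The risk ratios above should not be read as estimates of bias in this trial. They show direction only, under an assumed true ratio of 2, assumed control rates of about 1% to 5%, and prevalent cases balanced between arms. The primary outcome definition, the sample size and the main inference are not affected. The point still deserves correction, because the condition is safety-relevant, the trial plans 30 sites, and the repair is nearly free.

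**What to change.** Reconcile the section 6.2 bullet, the Note and the Appendix 3 option, so that each treats previous infection in one way and current infection in one way. Which rule applies is for the investigators to decide. If current infection is barred, the Appendix 3 option needs removal or a stated purpose. If it is not barred, the Note needs to say so.

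In sections 3.6 and 10.2.4, define the C. difficile outcome as infection with onset after randomisation, or else flag infections present at baseline and report them separately.

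The cost is a wording amendment and possibly one eCRF option. If the stricter reading is kept, a very few patients become ineligible.

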## 7 TRIAL PROCEDURES

#### 7.1 Screening and recruitment

Screening/Identification methods: The hospital research team or treating clinician will identify potentially eligible patients from intensive care units, surgical wards, radiology reports and infection service consultations. This will be done by reviewing patient records daily as a collaboration between research nurses and local investigators, including Associate Principal Investigators (APIs). Site teams will be encouraged to setup groups on approved platforms to communicate between themselves to facilitate participant identification. The research team will work closely with clinicians at each site to optimise screening and recruitment procedures for their local circumstances. Routine imaging and surgical findings will be used to inform eligibility. A clinician delegated to perform this task will confirm eligibility. Screening forms will be completed at all participating sites and will be used to capture numbers of ineligible or non-consenting patients at each site. High level data (age, sex, ethnicity and post-code) will be collected for those eligible but who do not participate to assess how representative the recruited trial population is, including to monitor equality and diversity. NIHR guidance on Equality, Diversity and Inclusion for study participants will be promoted.

**Recruitment:** Patient identification will be as close to clAl diagnosis as possible to limit recruitment bias. However, randomisation will take place after eligibility is confirmed as per the trial inclusion criteria (see 6.1). A clinician or a member of the research team will invite the eligible patient to consider joining the study. The patient will be provided with an invitation letter and a detailed PIS which will explain the risks and benefits of trial participation clearly in text form. Potential participants will be given a contact phone number, so they can ask questions of clinical staff and to discuss the trial with friends/family prior to agreement to take part. Sufficient time (within the time available prior to patient randomisation being required) will be given to patients to consider their participation in the trial. Research staff will obtain written informed consent by an appropriately trained research clinician or research nursing staff. If any eligible participant agrees to participate specific consent will be sought to enable the sharing of identifiable data with York Trials Unit (YTU) as part of the study in order to facilitate the collection of outcome data.

A proportion of potential participants may be sedated and therefore lack capacity to make an informed decision about their participation in the research project. The clinical and/or research team will assess capacity as per their usual procedures for receiving consent for a trial and decide as to whether the participant has capacity to consent prospectively or if a consultee agreement should be sought. In these instances, consent may be obtained at sites in England, Wales and Northern Ireland via a Personal Consultee (an individual who has a personal relationship with the patient; for example, relatives, carers or friends) or Nominated Consultee (a professional who is independent of the study). Appropriate Nominated Consultees will be identified at all of these sites for instances where a Personal Consultee is not available or decides they are unable to act in this capacity; in line with national guidance, as it applies to regions of the UK e.g. MCA (Department of Health, 2005) and Department of Health guidance (Department of Health, 2008). The nominated consultee will preferably be GCP trained but consultant level clinicians independent of the clinical research team without GCP training will also be able to act as a Nominated Consultee. At sites in Scotland, consent may be obtained from a welfare guardian, welfare attorney or if neither of those is available a close relative; in line with the Adults Incapacity Act (Scotland, 2000). The person providing consent will be provided with all study information and given the opportunity to ask questions and discuss the study before making a decision on whether they think the patient would want to take part and if it is in their best interest to do so. If they agree, their written agreement for the patients' inclusion into the trial will be recorded. Written consent to continue in the study will be sought from the participant at the first appropriate opportunity once they regain capacity. In the interim, efforts will be made to involve participants who, temporarily or permanently, lack the capacity to decide to be involved in the study. Appropriate information will be communicated to the participant and updated as their understanding changes. At all times the study team will act in accordance with the participant's best interests. On rare occasions, participants who have lacked capacity to consent may be discharged prior to providing written consent themselves. Should this situation arise, the trial team will make every effort to

discuss the trial with the patient and the patient's clinical care team at the earliest opportunity. We will seek consent from patients to access their summary care record, and to access medical notes from patients admitted to another NHS hospital.

## 7.1.1 Payments, rewards and recognition for study participants

Participants will be given an unconditional £20 voucher as a goodwill gesture with each follow-up questionnaire at 30, 90 and 180 days.

## 7.1.2 Quality control/assurance procedures

YTU will be responsible for the quality control/ assurance procedures.

## 7.2 The randomisation scheme

Participants will be individually randomised 1:1 between 28-days antibiotics and standard care antibiotic duration using stratified block randomisation with randomly varying block sizes. Stratification will be by: post-operative cIAI vs. non post-operative cIAI, surgical source control procedure vs. no surgical source control procedure and ICU stay vs. no ICU stay within 10 days of randomisation.

## 7.2.1 Method of implementing the randomisation/allocation sequence

Randomisation will occur within the first 10 days of antibiotic treatment for cIAI, and will be implemented using a web-based system designed and developed by the data management team at YTU. This system will be accessed by clinical research staff involved in patient recruitment at recruiting sites (as detailed in the site delegation log) and will be accessible 24 hours a day and 7 days a week. Prior to randomisation, research staff at recruiting sites will be required to enter the following key information; participant identification number, date of birth, participant contact details (to facilitate follow up), confirmation that the participant meets each of the eligibility criteria and the information required for stratification. The allocation sequences (one for each stratum) will be designed by the trial statistician. The actual sequences embedded in the randomisation system will be generated by a separate YTU statistician independent of the TMG, using a random number seed that will be concealed from all members of the trial team for the duration of the trial. Following randomisation, the research team at the site where the randomisation took place (including the PI, research nurses and pharmacists) will be notified of the treatment allocation by email. Each time a patient is randomised, the CI and central trial management team at YTU will also be notified by email.

## 7.3 Blinding

This is an unblinded trial with both treating clinicians and participants aware of treatment allocations.

## 7.4 Emergency unblinding

Not applicable

## 7.5 Baseline data

Data required prior to being eligible for study entry include:

- Full blood count demonstrating the patient has elevated or low neutrophils.
- Radiological investigation (e.g., CT scan/ultrasound scan/X-ray) consistent with a cIAI.

These will be undertaken as part of routine clinical practice and are not therefore trial specific procedures.

A full breakdown of data which will be collected at baseline is provided in Appendix 3.

